5.3. Intertreatment Period

Intertreatment period visits occur every 30 days after the previous visit in Part A and every 90 days after the previous visit in Part B.

At each ITP_nV_n (Part A) or ITPE_nV_n (Part B) an evaluation of the need for (re-)treatment should be done. In case the patient is not in need of (re-)treatment, assessments for ITP_nV_n (Part A) or ITPE_nV_n (Part B) should be performed as listed below and per the General Schedule of Assessments for Part A (Table 1) or for Part B (Table 2). However, in case the evaluation shows that the patient is in need of (re-)treatment and is also eligible for (re-)treatment, the assessments according to TP_nV1 (Part A) or TPE_nV1 (Part B) are to be performed instead (see Section 5.2). If an ITP visit for Part A is scheduled within 14 days of the EoA visit, then the EoA visit should be performed instead.

The following assessments will be performed in Part A:

- Assessments of disease severity – the MG-ADL scale should be administered before the QMG scale
- Suicidality assessment
- Physical examination
- Weight will only be measured in case there is an obvious weight change compared to the last weight assessment
- Vital signs
- ECG
- Clinical laboratory tests. Patients need to be fasted at least 8 hours prior to sampling
- Urinalysis

- Urine pregnancy test (only for women of childbearing potential, see [DEFINITION OF TERMS](#))
- Pharmacodynamic biomarkers (anti-AChR antibodies in AChR-Ab seropositive patients only, total IgG and subtypes [IgG1, IgG2, IgG3 and IgG4], and anti-MuSK antibodies in MuSK-Ab seropositive patients only)
- Review of concomitant medication and rescue therapy
- Assess AEs, if any

The following assessments will be performed in Part B:

- Assessments of disease severity (MG-ADL scale)
- Vital signs
- ECG
- Urine pregnancy test (only for women of childbearing potential, see [DEFINITION OF TERMS](#))
- Review of concomitant medication
- Assess AEs, if any

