(Hospital admissions and/or surgical operations planned before a trial are not considered SAEs or if the illness or disease, which caused hospitalization, existed before the patient was enrolled in the trial, provided that it did not deteriorate in an unexpected way during the trial. However, the condition for which the surgery is required may be an AE.)

- Results in persistent or significant disability or incapacity, OR
- Is a congenital abnormality or birth defect

- Other: Medically significant events, which do not meet any of the criteria above, but may jeopardize the patient and may require medical or surgical intervention to prevent 1 of the other serious outcomes listed in the definition above. Examples of such events are blood dyscrasias (eg, neutropenia or anemia requiring blood transfusion, etc.) or convulsions that do not result in inpatient hospitalization

Suspected Unexpected Serious Adverse Reactions (SUSARs) and Unexpected Adverse Reactions: Any suspected adverse reaction that is serious, unexpected, and considered to be related to drug exposure is defined as a SUSAR.

An unexpected AE is any adverse drug event, which is not listed in the current IB or is not listed at the specificity or intensity that has been observed.

Suspected adverse reaction means any AE for which there is a reasonable possibility that the drug caused the AE.

An untoward and unintended post-dosing response to a non-trial drug is, by definition, not a SUSAR, but is, however, an AE.

Each AE is to be evaluated for duration, severity, seriousness and causal relationship to efgartigimod or trial procedures. The action taken with the investigational drug and the outcome of the event must also be recorded.

Treatment-emergent adverse event (TEAE): Any AE temporally associated with the use of efgartigimod, whether considered related to efgartigimod or not. TEAEs are recorded from the start of efgartigimod administration, until completion of the patient's last visit.

Overdose

For the purposes of this trial, exceeding the dosage requirements specified in this protocol (see Section 6.1) represents an overdose. In case of suspected overdose, the patient should be treated according to standard medical practice based on the investigator's judgment.

Severity

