2.2 PHASES, PERIODS AND TIME POINTS

2.2.1 *Phases and periods*

All events and assessments will be allocated to phases and periods (see Table 1). A patient can start in 1705 in an inter-treatment period or in a cycle, depending on the patient status regarding the need for (re-)treatment upon roll-over. Each period following ITPO coincides with a cycle and includes the 4 administrations of efgartigimod and the inter-treatment period (ITP) visits. The length of the ITP is patient specific and can differ between the different periods. The number of patients may decline for each subsequent cycle.

	Statistical Analysis Plan	
ARGX-113-1705	Final Analysis	Final 1.0 of 20SEP2022

Table 1: phase/period definition

Phase	Period	Start	End
Treatment	ITP0	Earliest of (date of signing the informed consent form (ICF) and date of roll-over), with 00:00 added as time part.	First administration date/time in cycle 1 – 1 minute
	Cycle 1	First administration date/time in cycle 1	First administration date/time in next cycle – 1 minute or if last cycle: date of last contact, with 23:59 added as time part
	Cycle n	First administration date/time in cycle n	First administration date/time in next cycle – 1 minute or if last cycle: date of last contact, with 23:59 added as time part
	Cycle x	First administration date/time in cycle x	Date of last contact, with 23:59 added as time part

AEs and concomitant medications will be allocated to phases and periods as described in sections 5.1.2 and 3.5.2 respectively. All other assessments will be allocated to phases and periods based on the assessment date/time.

In case of (partially) missing date/time fields disabling allocation or date(time) equal to dosing date(time), information from visit label and protocol schedule of assessments (SoA) will be used to allocate to the correct period. If this is not possible, assessments will be allocated to the first possible cycle (not ITP0) unless the available parts of the assessments start or stop date/time provide evidence the assessments did not occur during that period.

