2.4 PRESENTATION OF RESULTS

2.4.1 Calculation of descriptive statistics and percentages

In tables by analysis visit, only analysis visits with at least 10 subjects (overall) will be shown.

For continuous variables, full descriptive statistics will only be presented if there are at least 2 non-missing observations. Alternatively, only the number of non-missing data points and mean are shown.

	
Statistical Analysis Plan
	

ARGX-113-1705
	
Final Analysis
	
Final 1.0 of 20SEP2022

Descriptive statistics will include the number of non-missing data points, the arithmetic mean, the standard deviation (SD), the median, minimum, Q1, Q3 and maximum.

Mean, median, Q1 and Q3 will be presented with one more decimal place than the individual values. SD will be presented with two more decimal places than the individual values. Minimum and maximum will be presented with the same number of decimal places as the individual values.

For event-type safety data, the number and percentage of patients with an event will be shown. The denominator will be all patients in the analysis set per treatment and cycle. All cycles will be shown, even if no events are present.

For frequency tabulations and cross-tabulations, the denominator will be all patients in the analysis set per treatment. For tables where results are shown by analysis visit, the denominator will be all patients in the analysis set per treatment and per analysis visit. Missing values will never be included in the denominator count when computing percentages. For cross-tabulations of post-baseline results versus baseline results, a ‘missing’ category will be shown for baseline results if applicable.

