2.4.3 Ordering in tables, figures and listings

For presentations by analysis visits, this analysis will only tabulate data collected from the first OLE cycle on. In case a patient starts with ITP0 visits, these will not be considered in the tables. Part B data will not be tabulated separately but will be allocated to cycles like part A data.

All tables will be presented per treatment and cycle, unless specified otherwise. If present, worst-case will be shown last. Cycles will be indicated as a subtitle or within the table like “Cycle n”.

Listings for general characteristics, results will be ordered by treatment and patient, unless specified otherwise.

All other listings will be ordered by treatment, patient, period, analysis visit and time point, unless specified otherwise.

In tables showing several parameters, each parameter will begin on a new page and parameters will be sorted alphabetically, within the parameter category if applicable.

Efgartigimod-efgartigimod group will always be shown first and then Placebo-efgartigimod.

	Statistical Analysis Plan	
ARGX-113-1705	Final Analysis	Final 1.0 of 20SEP2022

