3. GENERAL CHARACTERISTICS ANALYSES

3.1 SUBJECT DISPOSITION

The following patient data will be tabulated:

- The number of patients in each analysis set
- The number and percentage of patients by country and investigator
- The number and percentage of patients for each period/analysis visit.
- The number and percentage of patients for each period/analysis visit who had a missed visit and who had a phone call visit due to COVID-19 (as documented in the CRF comment).
- Descriptive statistics and tabulation in weeks of the cycle duration (see section 2.2.1), calculated as cycle end date – cycle start date + 1 day
- Descriptive statistics of the study duration, calculated as study end date – study start date + 1 day.
- Frequency tabulation of the study duration per 6-monthly period, showing the number and percentage in each category and additionally cumulative number and percentages. Categories are defined as follows: <6 months (< 168 days); 6 to <12 months (168 - 350 days); 12 to <18 months (351 - 532 days); 18 to <24 months (533 - 715 days); 24 to <30 months (716 - 897 days); 30 to <36 months (898 - 1080 days); 36 to <42 months (1081 - 1262 days).
- The number and percentage of patients who completed or discontinued the study as documented on the study termination page and the number and percentage of patients for each study discontinuation reason.
- The number and percentage of patients who completed or discontinued the study as documented on the study termination page and the number and percentage of patients for each study discontinuation reason by cycle.
- The number and percentage of patients who completed or discontinued the treatment as documented on the end of treatment page and the number and percentage of patients for each treatment discontinuation reason.
- The number and percentage of patients who completed or discontinued the treatment as documented on the end of treatment page and the number and percentage of patients for each treatment discontinuation reason by cycle.

All information collected in the CRF concerning study and treatment discontinuation will be listed.

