5. SAFETY ANALYSES

5.1 ADVERSE EVENTS

5.1.1 *Available data*

Adverse events (AEs) are coded into system organ classes and preferred terms using the MedDRA version 24.1 (SEP2021). AEs were graded using the National Cancer Institute (NCI) Common Terminology Criteria for Adverse Events (CTCAE) version 5.0. For each AE, start and stop date/times are collected as well as severity, a seriousness flag, treatment relatedness, relatedness to procedures, action taken towards the study drug and outcome.

5.1.2 *Derivation rules*

Based on their start date/time, AEs will be allocated to the analysis period during which they started. Each AE will therefore be reported in only one period. Periods are defined in section 2.2.1. In case the AE start date/time is incomplete or missing and the AE could consequently be allocated to more than one period, AE will be allocated to the first possible cycle unless the available parts of the AE start or stop date/time provide evidence the assessments did not occur during that period.

Event rates per patient years of follow-up (PYFU) will be defined as the number of events divided by the sum of follow-up time (i.e. duration of treatment phase) of all participants per treatment expressed in years.

A death case is defined as an AE with outcome ‘fatal’.

Adverse events of special interest will be defined using MedDRA SOC ‘Infections and infestations’.

Infusion-related reactions (IRR) will be defined as all AEs with a MedDRA preferred terms that are listed in either:

- MedDRA Hypersensitivity SMQ broad selection
- MedDRA Anaphylactic reaction SMQ broad selection
- MedDRA extravasation events (injections, infusions and implants) SMQ broad selection, excluding implants

AND occurring within 48 hours of an infusion, or within 2 days in case no AE start time is available.

An AE for which the study drug was discontinued is defined as an AE with action taken ‘drug withdrawn’.

Treatment-relatedness will be dichotomised as follows in tables:

- Treatment-related: related, probably related, possibly related or missing
- Not treatment-related: not related, unlikely related, not applicable

	
Statistical Analysis Plan
	

ARGX-113-1705
	
Final Analysis
	
Final 1.0 of 20SEP2022

AE onset and duration will be calculated as follows when start and stop dates are fully known

- AE onset day (vs. first administration)

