5.1.3 Presentation of results

Adverse events occurring in ITP0 will only be listed. AEs will be tabulated by AChR-Ab status and overall and within AChR-Ab status, by cycle and overall.

An overview table will show the number and percentage of patients with at least one event, the number of events and event rates per patient years of follow-up for the following:

- TEAEs
- Serious TEAEs
- Grade ≥ 3 TEAEs
- TEAEs of special interest
- IRR events
- Fatal TEAEs
- Treatment-related TEAEs according to the Principle Investigator
- Procedures-related TEAEs according to the Principle Investigator
- Serious treatment-related TEAEs
- TEAEs for which the study drug was discontinued

Summary tables by MedDRA system organ class and preferred term will show the number and percentage of patients with at least one event. The table of TEAEs will additionally show the number of events.

	
Statistical Analysis Plan
	

ARGX-113-1705
	
Final Analysis
	
Final 1.0 of 20SEP2022

Separate tables will be prepared for the following TEAEs:

- Serious TEAEs
- Non-serious TEAEs
- Grade ≥ 3 TEAEs
- IRR events
- Treatment-related TEAEs
- Procedures-related TEAEs
- Serious treatment-related TEAEs
- Serious IRR events
- TEAEs for which the study drug was discontinued

All AEs, including pre-treatment events will be listed.

COVID related events (events with preferred term COVID-19, COVID-19 pneumonia, suspected COVID-19 and coronavirus infection) will be listed. This listing will include all collected AE information and additionally the cycle, onset since first efgartigimod dose, onset since last efgartigimod dose before AE onset, last total IgG before AE onset, the last percent change in total IgG before AE onset and the time when that reported total IgG was taken compared to AE onset.

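### Overall adverse-event rates per patient-year count events from the first 1705 dose but divide by time from consent or roll-over, so they are low by ITP0's share of follow-up

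*SAP*

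**What the plan says.** **Denominator.** SAP 5.1.2 takes the number of events "divided by the sum of follow-up time (i.e. duration of treatment phase) of all participants per treatment expressed in years". SAP 2.2.1, Table 1, shows only one phase, Treatment, and puts ITP0 first within it. ITP0 starts at the "Earliest of (date of signing the informed consent form (ICF) and date of roll-over), with 00:00 added as time part" and ends one minute before the first administration in Cycle 1. The last cycle ends at the date of last contact.

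**Numerator.** SAP 5.1.3 states: "Adverse events occurring in ITP0 will only be listed". The overview table gives rates for treatment-emergent events (all, serious, grade 3 or higher, of special interest, fatal, related, leading to discontinuation) and for infusion-related reactions. Protocol 7.2.1 says "TEAEs are recorded from the start of efgartigimod administration". SAP 5.1.2 requires an infusion-related reaction to fall within 48 hours of an infusion.

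**ITP0 elsewhere.** For presentations by analysis visit, SAP 2.4.3 says: "In case a patient starts with ITP0 visits, these will not be considered in the tables". No corresponding sentence covers person-time, and SAP section 6 records no changes to the planned analysis.

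**By cycle.** SAP 5.1.3 asks for adverse events by cycle and overall. SAP 2.4.1 gives a by-cycle denominator for percentages: "The denominator will be all patients in the analysis set per treatment and cycle". That is a count of patients. The person-time rule is written per treatment over the whole phase.

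**The concern.** Numerator and denominator cover different time windows. A rate per patient-year is interpretable only if an event occurring at any point in the counted person-time would also be counted. Here a patient who rolls over without needing treatment adds days or months to the denominator before any event of theirs can reach the table. The error can only lower the rate, which favours the drug.

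Long-term safety is the primary objective, and follow-up varies up to three years, with some patients leaving Part B for ARGX-113-2002. The rate per patient-year is the overview measure that adjusts for unequal follow-up, so it is likely to be quoted and compared with other sources. In the placebo-efgartigimod column, ITP0 also precedes any efgartigimod exposure, yet it adds time to that column and to Total efgartigimod. If ITP0 time differs between the two columns, their rates are distorted by different amounts. The documents do not show whether it does.

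**Working it through.** The plan states no event rate, person-time or ITP0 duration, so there is no figure of its own to reproduce. The check is algebra followed by a range of assumptions.

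**Set-up.** For each patient in the safety set, let T be the treatment-phase time (consent or roll-over to last contact) and I the part of T spent in ITP0. Let E be the number of events from the first 1705 dose onward.

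- Rate as written: E / ΣT
- Rate with matched windows: E / Σ(T − I)
- Ratio, written to matched: Σ(T − I) / ΣT = 1 − ΣI / ΣT

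The relative shortfall is ΣI / ΣT, ITP0's share of total follow-up. It does not depend on the event type or on the true rate.

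**Inputs.** With f the share of patients who start in ITP0, L their mean ITP0 length and T̄ the mean treatment-phase time, the shortfall is f × L / T̄. None of the three is given. Assumed ranges:

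- f: 20% to 60%. SAP 2.2.1 allows a start either in an inter-treatment period or in a cycle.
- L: 30 to 120 days, that is, one to four of the visit intervals in Protocol 5.3 ("Intertreatment period visits occur every 30 days after the previous visit in Part A").
- T̄: 365, 730 or 1095 days. 1095 days is the protocol maximum.

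**Results.**

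| f, L | f × L (days) | T̄ = 365 | T̄ = 730 | T̄ = 1095 |
|---|---|---|---|---|
| 20%, 30 days | 6 | 1.6% | 0.8% | 0.5% |
| 40%, 60 days | 24 | 6.6% | 3.3% | 2.2% |
| 60%, 120 days | 72 | 19.7% | 9.9% | 6.6% |

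For example, 24/365 = 6.58%, so a matched rate of 100 events per 100 patient-years would be reported as 93.4. At 730 and 1095 days it would be reported as 96.7 and 97.8.

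**Limits.** For a patient dosed at the roll-over visit, ITP0 is less than a day and the bias is essentially nil. At the other end, Protocol 5.2.1 lets a Part A treatment period start as late as day 336, so an individual ITP0 can reach about 335 days even if the first dose is given in Part A.

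**Simulation check.** I simulated 100,000 patients with follow-up uniform on 200 to 1095 days. Half had no ITP0, the other half an ITP0 uniform on 0 to 180 days, and the true post-dose rate was 4 per patient-year. ITP0's share of follow-up was 6.9%. The rule as written gave 3.73 and the matched rule 4.00, a ratio of 0.931 = 1 − 0.069.

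**The case against.** The best counter-argument is that nobody would program it this way. SAP 5.1.3 refers to listed events from before treatment, and the analysis-visit table in SAP 2.2.4 has no ITP0 row, so a programmer might start the treatment phase at Cycle 1. That could happen, but it would depart from Table 1, where the phase is defined. If two programmers can reasonably differ, the sentence is needed anyway.

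A second argument is that ITP0 is legitimate follow-up for patients who had efgartigimod in 1704. Had the SAP also counted their ITP0 events, that would be a coherent rate with a different meaning. It excludes those events, so the mismatch remains, and the argument does not apply to patients who had placebo in 1704.

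The points on size are fair. All three inputs are assumed, and the 19.7% figure combines the least favourable value of each. This is the final analysis of a trial lasting up to three years, and longer follow-up shrinks the effect. Incompletely dated events go to the first possible cycle, which may move a few ITP0 events into Cycle 1 and offset the bias slightly.

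The points on reach also stand. The protocol's endpoint is incidence and severity, summarised in frequency tables; its statistics section names no person-time rate. The analysis is descriptive. A careful reader could rebuild the matched rates from event counts and cycle durations, though few will.

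Finally, cycle duration is the natural denominator for a by-cycle rate. I agree: that part is missing detail, not an error.

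**Conclusion.** The concern holds. Followed as written, the SAP gives overall rates per patient-year that are too low by ITP0's share of follow-up, apart from a possible slight offset from incompletely dated events. The mechanism and direction follow from the SAP's own definitions; the size cannot be known from the documents. Under the stated assumptions the understatement is a few per cent in the middle case and larger only if many patients start in ITP0, stay there for months and have short follow-up.

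The damage is confined to the rates in the adverse-event overview table (14.3.1.1). Event counts, patient counts, percentages and the tables by system organ class and preferred term stand, and no test depends on the rates. It should be fixed because the error favours the drug in a long-term safety trial and correcting it costs very little. The unspecified by-cycle denominator is a secondary gap.

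**What to change.** In SAP 5.1.2, define follow-up time for the rates as running from the first efgartigimod administration in 1705 (start of Cycle 1) to the end of the last cycle, in the safety analysis set, with ITP0 excluded. Add that a rate shown for cycle n uses the summed duration of cycle n among patients who entered it. SAP 3.1 already derives what is needed ("Descriptive statistics and tabulation in weeks of the cycle duration").

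One programming caution: SAP 3.1 adds one day to each cycle's duration, and Table 1 ends a cycle one minute before the next cycle's first dose, normally on the same calendar date. Adding up cycle durations would therefore count that date twice. Compute the overall follow-up as a single span.

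Counting ITP0 events in the numerator would also match the windows, but the rate would then need a different label, because those events are not treatment-emergent in 1705 and, for patients on placebo in 1704, precede any exposure.

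The cost is one or two sentences and one programming change. Rates will be slightly higher and may not match interim outputs if those used the same definition, which a footnote can explain.
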